3.4.3.4 Sensitivity Analysis

If there is a difference between the number of patients in the ITT and the SAF population, the outputs for OS and PFS will be repeated on the ITT population using the date of enrollment as start date. Patients without any post-enrollment data will be censored at the date of enrollment plus 1 day.

3.4.4 Subgroup Analyses

The OAK-LIKE Subgroup is defined as patients with the next characteristics:

- ECOG Performance status of 2: no
- Patients with previous anti-PD-1, anti-PD-L1, or ant-CTLA-4 therapy: no
- Presence of untreated CNS metastases at baseline: no
- Renal impairment (creatinine clearance < 30 mL/min (CKD-EPI)): no
- Liver
 - AST and ALT ≤ 2.5 times the upper limit of normal (ULN), with alkaline phosphatase ≤ 2.5 ULN OR
 - AST and ALT ≤ 1.5 x ULN, with alkaline phosphatase > 2.5 x ULN
- HIV-positive: no
- HBV/HVC status: not active

- History of autoimmune disease: no
- Concomitant steroid treatment ongoing at baseline: no

OS and PFS results across subgroups will be examined in the following subgroups. Subgroups with ≤ 10 patients will not be included.

- OAK-LIKE
- Demographics:
 - Age (<, \geq 65 years),
 - Sex,
 - Region (EMEA, Asia, LATAM),
 - Smoking status (never, current/previous)
- Baseline disease characteristics:
 - Histologic subtype (squamous, non-squamous),
 - ECOG performance status at baseline (0/1, 2),
 - Brain metastases at baseline (yes, no)
 - Liver metastases at baseline (yes, no),
 - History of autoimmune disease (yes, no),
 - Prior anti-PD-1 therapies (yes, no),
 - Renal impairment (eGFR<, \geq 60 mL/min/m²),
 - EGFR positive at baseline (yes, no),
 - ALK positive at baseline (yes, no),
 - Active hepatitis B or C at baseline (positive, negative),
- PD-L1 status (Central):
 - PD-L1 Expression on TC (<1%, \geq 1%, [1-50[%], \geq 50%)
- PD-L1 status (Local):
 - PD-L1 Expression on TC (<1%, \geq 1%, [1-50[%], \geq 50%)
- PD-L1 (BEP):
 - PD-L1 Expression on TC (<1%, \geq 1%, [1-50[%], \geq 50%)
 - Yes vs No
- PD-L1 (OAK-LIKE/BEP):
 - PD-L1 Expression on TC (<1%, \geq 1%, [1-50[%], \geq 50%)
 - Yes vs No

Summaries of OS and PFS, including Kaplan-Meier estimates of median OS and PFS, OS rate at 6, 12, 24 and 36 months, PFS rate at 6, 12 and 24 months will be produced separately for each level of the subgroup. For the primary analysis, only the rate at 6 and 12 months will be estimated.

3.5 SAFETY ANALYSES

Safety summaries will be produced on the safety population.

3.5.1 Exposure of Study Medication

Treatment exposure, including treatment duration and number of doses received will be summarized as both continuous and categorical variables.

3.5.2 Primary Safety Endpoints

The primary endpoints are the following AE categories:

- Serious AE related to study drug
- Immune-related AE related to study drug

Incidence rates will be provided along with the corresponding 95% Pearson-Clopper CIs. Additionally, both categories will be summarized by SOC, PT and NCI CTCAE grade.

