6.4 PRIMARY ENDPOINT ANALYSIS

All safety analyses will be run on the Safety Analysis set, defined as all enrolled patients who had at least one administration of atezolizumab. The primary analysis will occur approximately 6 months after the last patient has been enrolled.

The incidence of SAEs related to atezolizumab and the incidence of irAEs related to atezolizumab will be summarized by incidence rates and 95% Pearson-Clopper confidence intervals.

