3.5.3 Adverse Events

Verbatim description of adverse events will be mapped to Medical Dictionary for Regulatory Activities (MedDRA) thesaurus terms and graded according to the NCI CTCAE v4.0. Summary tables will include only the treatment emergent adverse events up to the data cutoff date.

The following Adverse Events will be summarized:

- All Adverse Events
- Treatment Related Adverse Events
- Grade ≥ 3 adverse events
- Serious Adverse Events
- Adverse events leading to Atezolizumab discontinuation
- Adverse events leading to Atezolizumab discontinuation or interruption
- Adverse Events with Fatal Outcome
- Adverse Events of Special Interest
- Treatment Related Adverse Events of Special Interest
- Serious Adverse Events of Special Interest
- Immune-Related Adverse Events

The AE tables will include the number and percentage of patients with at least one AE, by MedDRA primary System Organ Classes (SOC) and MedDRA Preferred Terms (PT) and by NCI CTCAE grade. A patient with more than one occurrence of the same adverse event in a particular SOC/PT will be counted only once in the total of those experiencing adverse events in that particular SOC/PT. For immune-related AE related to study drug, similar summary will be provided by AESI category and PT. Summary tables displaying number of patients with at least one AE by PT will also be provided.

Deaths reported during the study treatment period and those reported during the follow-up period after treatment completion/discontinuation and causes of death will be summarized by treatment arm.

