3.5.4 Time to first onset of AE

The time to first onset of specific AE (AESI) (in months) will be analyzed and be summarized using Kaplan Meier methodology.

The time to first onset of any specific AE is defined as the time (in months) from initiation of study treatment until the date of first onset of a specific AE. Patients without any occurrence of specific AE will not be counted.

The analysis described above will be conducted for the following categories of AEs:

- AESI,
- Immune-related AE

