3.5.7 Subgroup Analyses

Safety summary tables and summary of AE by SOC/PT will be repeated for the following subgroups:

- OAK-LIKE Population
- Demographics:
 - Age (<, ≥ 65 years),
 - Age (<, ≥ 80 years),
 - Region (Europe, Asia, LATAM)
- Baseline disease characteristics:
 - Histologic subtype (squamous, non-squamous),
 - ECOG performance status at baseline (0/1, 2),
 - Brain metastases at baseline (yes, no)
 - Liver metastases at baseline (yes, no),
 - History of autoimmune disease (yes, no),
 - Prior anti-PD-1 therapy (yes, no),
 - Renal impairment (eGFR $<$, ≥ 60 mL/min/m²),
 - EGFR positive at baseline (yes, no),
 - ALK positive at baseline (yes, no),
 - Active hepatitis B or C at baseline (positive, negative),

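### Safety subgroup tables set crude percentages side by side although time at risk differs, so event rates in frailer subgroups such as ECOG 2 can be understated

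*SAP*

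**What the plan says.** SAP 3.5.2 names the two primary endpoints and states that "Incidence rates will be provided along with the corresponding 95% Pearson-Clopper CIs". Protocol 6.4 has the same measure: the two incidences "will be summarized by incidence rates and 95% Pearson-Clopper confidence intervals". A Clopper-Pearson interval belongs to a binomial proportion, so the word rate here means treated patients with at least one event divided by all treated patients. SAP 3.5.3 is explicit for the other tables: "The AE tables will include the number and percentage of patients with at least one AE". SAP 3.5.7 then provides that "Safety summary tables and summary of AE by SOC/PT will be repeated for the following subgroups"; the list includes ECOG 0/1 against 2, brain metastases, autoimmune history, prior anti-PD-1 therapy and the OAK-like group.

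Exposure appears only descriptively, in SAP 3.5.1: "Treatment exposure, including treatment duration and number of doses received will be summarized as both continuous and categorical variables". It is not tied to event counts. SAP 3.5.4 plans a Kaplan-Meier analysis of time to first AESI and irAE, but "Patients without any occurrence of specific AE will not be counted". Protocol 6.6.1 has a wider Kaplan-Meier plan (AEs, SAEs, Grade 3–5 AEs and irAEs), but section 3 of the SAP says that the SAP's analyses replace the protocol's. Neither document specifies a patient-time denominator.

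**The concern.** Time at risk is unequal by design. Treatment has no fixed length; it ends with loss of benefit, toxicity, withdrawal or death (Protocol 3.1). Routine SAE and AESI collection then runs for 90 days after the last dose or until new anti-cancer therapy (Protocol 5.1). With about 18 months of recruitment (Protocol synopsis) and a primary analysis about 6 months after the last enrolment (SAP 2.4), potential follow-up at that analysis ranges from about 6 to 24 months. A patient who stops or dies early has less time in which an event can be recorded.

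Protocol 1.3 explains that eligibility was widened to patients whom earlier studies screened out, including ECOG 2, prior anti-PD-1 therapy, untreated CNS metastases and autoimmune disease. Readers will therefore look at the subgroup columns together. Where prognosis differs, as with ECOG status, a lower percentage may reflect shorter observation rather than less toxicity.

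**Working it through.** **The plan's own figure.** SAP Table 1 gives the precision for 600 patients. At 10%, 0.10 ± 1.96 × √(0.10 × 0.90/600) = 0.10 ± 0.024, that is 7.6% to 12.4%, as printed. This confirms that the denominator is patients, not time. (That is the normal-approximation interval; the exact interval for 60/600 is 7.72% to 12.68%. The label is a separate matter.)

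**Model.** Event hazard h per month is constant while at risk. Death hazard is d = ln 2/median OS. The hazard of stopping treatment for reasons other than death is s = ln 2/median treatment time. The at-risk window ends at death or 3 months after stopping. Expected time at risk per patient is

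M = (1 − e^(−3(h+d)))/(h+d) + e^(−3(h+d))/(h+d+s).

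The crude percentage is h × M. The rate per 100 patient-years is 1200 × h.

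**Inputs.** Only the OS median of 13.8 months for ECOG 0/1 is in the documents (Protocol 1.2.1.4, atezolizumab arm of the phase III comparison with docetaxel). Every other input is an assumption, varied below.

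| Group (median treatment / OS, months) | h | M (months) | Crude h × M | Per 100 patient-years |
|---|---|---|---|---|
| ECOG 0/1 (4 / 13.8) | 0.015 | 2.72 + 3.45 = 6.17 | 9.3% | 18 |
| ECOG 2 (1.5 / 4), same hazard | 0.015 | 2.29 + 0.87 = 3.17 | 4.7% | 18 |
| ECOG 2 (1.5 / 4), 1.5-fold | 0.0225 | 2.27 + 0.84 = 3.11 | 7.0% | 27 |
| ECOG 2 (2 / 6), 1.5-fold | 0.0225 | 2.46 + 1.36 = 3.82 | 8.6% | 27 |
| ECOG 2 (3 / 8), 1.5-fold | 0.0225 | 2.56 + 2.12 = 4.68 | 10.5% | 27 |
| ECOG 2 (3 / 9), 1.5-fold | 0.0225 | 2.59 + 2.24 = 4.84 | 10.9% | 27 |

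The true ratio is 1.5 in the last four rows. The crude ratio is 7.0/9.3 = 0.75, 8.6/9.3 = 0.92, 10.5/9.3 = 1.13 and 10.9/9.3 = 1.17. Administrative cut-off T changes little: multiplying the second term of M by 1 − e^(−(h+d+s)(T−3)) and averaging over T from 6 to 24 months gives 8.7% for ECOG 0/1 against 7.0%, 8.5%, 10.2% and 10.6%.

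**When the order reverses.** A simpler model has one exit hazard μ = 1/(mean time to leaving the window) and crude percentage λ/(λ+μ) × (1 − e^(−(λ+μ)T)), averaged over the same T. With a reference rate of 14.4 per 100 patient-years, the crude order is wrong whenever the true rate ratio lies between 1 and about 1.23 (mean exit 8 against 6 months), 1.72 (8 against 4) or 2.24 (8 against 3). These limits hardly move for reference rates from 7.2 to 24.

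**Test of the remedies.**

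- *A single exposure-adjusted rate.* Give both groups the same front-loaded hazard, 0.03 per month for 3 months and 0.0075 after. ECOG 0/1 (4 / 13.8) has 2.67 months at risk early and 3.40 later: 1200 × (0.03 × 2.67 + 0.0075 × 3.40)/6.07 ≈ 20.9. ECOG 2 (1.5 / 4) has 2.25 and 0.85: 1200 × (0.03 × 2.25 + 0.0075 × 0.85)/3.09 ≈ 28.6. The excess is spurious. By interval, both groups show 1200 × 0.03 = 36 and then 1200 × 0.0075 = 9.
- *Cumulative incidence with death competing.* h/(h+d) × (1 − e^(−t(h+d))), with ECOG 2 at the 1.5-fold hazard and OS of 4 months, gives 7.4% (ECOG 0/1) against 7.9% (ECOG 2) at 6 months, but 12.5% against 10.4% at 12 months. It still depends on early death.

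**The case against.** The strongest reply is that the study is noncomparative (Protocol 3.3.2), its subgroups are exploratory (Protocol section 2) and SAP 3.5.7 plans no test between them. The overall percentage answers the stated endpoint and matches the basis of the sample size. This stands. A reader might infer that the primary endpoints themselves are invalid; the documents do not support that. The weakness is in the subgroup display.

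A reader might also infer that ECOG 2 will look safer than it is. The documents give neither treatment duration, survival nor event rates by ECOG status, and with milder assumptions the order is right and only the contrast shrinks.

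Third, an exposure-adjusted rate is not the truth either: the front-loaded example shows that it can mislead when the hazard is not constant. This also stands, and it is why rates by interval are needed.

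Fourth, routine collection is not the whole story. After the window, investigators are still asked to report SAEs and AESIs that they believe related (Protocol Appendix 1, footnote x; for SAEs also Protocol 5.6). Those events must not enter a numerator whose patient-time has already stopped.

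Finally, the wording of SAP 3.5.7 may be broad enough to include exposure by subgroup. That would help a reader, but it is not an adjustment.

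**Conclusion.** The point holds for the subgroup tables. Crude percentages are sound descriptions of treated patients overall, but they understate a frailer subgroup relative to a fitter one when its time at risk is shorter, and nothing in the SAP corrects for this. SAP 3.5.4 would be the natural place, but once event-free patients are removed it describes timing only among patients who had the event, and related SAEs are not in it.

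The size is illustrative. For a true 1.5-fold rate, the crude ratio lay between 0.75 and 1.17 under the assumptions shown. These are constant hazards within each group, a 3-month tail after stopping, and assumed ECOG 2 medians of 1.5 to 3 months on treatment and 4 to 9 months of survival. Attenuation follows whenever the frailer group has less time at risk; reversal is possible but cannot be predicted from the documents.

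**What to change.** Keep the crude percentages. In SAP 3.5.2 and 3.5.7 add, for both primary endpoints, overall and by subgroup:

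- Patients with a first event per 100 patient-years at risk, with an exact Poisson 95% CI. Patient-time runs from first dose to the earliest of first event, death, new anti-cancer therapy, 90 days after last dose, or cut-off. State this window in the SAP, since Protocol 5.1 includes the stop at new therapy and Protocol 5.3.1 does not mention it.
- The same rates by interval (for example 0–3, 3–6 and over 6 months), because a single rate assumes a constant hazard.
- Exposure tabulated by subgroup.
- A separate listing of related events reported after the window, kept out of the numerator.

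In SAP 3.5.4, keep event-free patients, censored at the end of their at-risk window, and add related SAEs. Cumulative incidence with death as a competing event may be shown as a description of absolute risk, but it should not be the basis for statements about event rates between subgroups.

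The cost is SAP wording and a few tables from dosing, event, therapy and death dates already collected. The price in assumptions is a rate taken as constant within each interval.

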3.5.3 Adverse Events

Verbatim description of adverse events will be mapped to Medical Dictionary for Regulatory Activities (MedDRA) thesaurus terms and graded according to the NCI CTCAE v4.0. Summary tables will include only the treatment emergent adverse events up to the data cutoff date.

The following Adverse Events will be summarized:

- All Adverse Events
- Treatment Related Adverse Events
- Grade ≥ 3 adverse events
- Serious Adverse Events
- Adverse events leading to Atezolizumab discontinuation
- Adverse events leading to Atezolizumab discontinuation or interruption
- Adverse Events with Fatal Outcome
- Adverse Events of Special Interest
- Treatment Related Adverse Events of Special Interest
- Serious Adverse Events of Special Interest
- Immune-Related Adverse Events

The AE tables will include the number and percentage of patients with at least one AE, by MedDRA primary System Organ Classes (SOC) and MedDRA Preferred Terms (PT) and by NCI CTCAE grade. A patient with more than one occurrence of the same adverse event in a particular SOC/PT will be counted only once in the total of those experiencing adverse events in that particular SOC/PT. For immune-related AE related to study drug, similar summary will be provided by AESI category and PT. Summary tables displaying number of patients with at least one AE by PT will also be provided.

Deaths reported during the study treatment period and those reported during the follow-up period after treatment completion/discontinuation and causes of death will be summarized by treatment arm.

3.5.4 Time to first onset of AE

The time to first onset of specific AE (AESI) (in months) will be analyzed and be summarized using Kaplan Meier methodology.

The time to first onset of any specific AE is defined as the time (in months) from initiation of study treatment until the date of first onset of a specific AE. Patients without any occurrence of specific AE will not be counted.

The analysis described above will be conducted for the following categories of AEs:

- AESI,
- Immune-related AE

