- b. Response will be assessed by the investigator using RECIST v1.1 (see [Appendix 2](#)) and modified RECIST (see [Appendix 3](#)). Patients who continue atezolizumab treatment beyond radiographic disease progression assessed per RECIST v1.1 will be monitored with a follow-up scan at the next scheduled tumor assessment when the scan frequency is every 6 weeks, and will be assessed by modified RECIST criteria (see [Appendix 3](#)) until treatment discontinuation. If the scan frequency is every 9 weeks (see [Appendix 1](#)), a follow-up scan is recommended at 9 weeks or earlier if clinically indicated.
- c. In those patients for whom tumor assessments are performed as part of local clinical practice and are available for report after PD or atezolizumab treatment discontinuation, best overall response (BOR) and PFS will be assessed from the first date of the new anticancer therapy to the end of the study per RECIST v1.1 and modified RECIST.

The primary objective of the study is to evaluate the long-term safety of atezolizumab. Long-term safety will be assessed by monitoring the nature, severity, duration, frequency and timing of atezolizumab-related SAEs and atezolizumab-related irAEs. An irAE is defined as any adverse event of special interest (AESI) associated with systemic corticosteroid use within 30 days of the onset date. All-causality AEs, all-causality SAEs, AEs and SAEs leading to atezolizumab interruption or discontinuation, and AESIs will also be reported, as well as causes of death, vital signs, physical findings and clinical laboratory results.

Secondary objectives will assess the efficacy of atezolizumab. The main efficacy objective will be to evaluate the OS rate 2 years after the first dose of atezolizumab.

Other efficacy objectives will include evaluation of OS, OS rate at 3 years, PFS, ORR, and DOR (additional efficacy assessments may occur on an exploratory basis). All antitumor response assessments will be based on RECIST v1.1 and modified RECIST.

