5. ASSESSMENT OF SAFETY

5.1 SAFETY PLAN

The safety plan for patients in this study is derived from clinical experience with atezolizumab in completed and ongoing studies. The anticipated important safety risks are outlined below (see Section 5.1.1).

Measures will be taken to ensure the safety of patients participating in this study, including the use of carefully chosen inclusion and exclusion criteria and close monitoring of patients during the study. Administration of atezolizumab will be performed in a monitored setting in which there is immediate access to trained personnel and adequate equipment and medicine to manage potentially serious reactions.

After initiation of study treatment, all adverse events will be reported until 30 days after the last dose of study treatment or until initiation of new anti-cancer therapy, whichever occurs first. SAEs and adverse events of special interest will continue to be reported until 90 days after the last dose of study treatment or until initiation of new anti-cancer therapy, whichever occurs first.

Guidelines for managing anticipated adverse events, including criteria for dosage modification and treatment interruption or discontinuation, are provided below (Section 5.1.2), in [Appendix 9](#) and in the Atezolizumab Investigator's Brochure. Refer to Sections 5.2–5.6 for details on safety reporting during the study.

Patients with active infection are excluded from study participation. In the setting of a pandemic or epidemic, screening for active infections (including SARS-CoV-2) prior to and during study participation should be considered according to local or institutional guidelines or guidelines of applicable professional societies (e.g., American Society of Clinical Oncology or European Society for Medical Oncology).

Severe COVID-19 appears to be associated with a CRS involving the inflammatory cytokines IL-6, IL-10, IL-2, and IFN- γ (86). If a patient develops suspected CRS during the study, a differential diagnosis should include COVID-19, which should be confirmed or refuted through assessment of exposure history, appropriate laboratory testing, and clinical or radiologic evaluations per investigator judgment. If a diagnosis of COVID-19 is confirmed, the disease should be managed as per local or institutional guidelines.

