6.6 OTHER SECONDARY ENDPOINT ANALYSES

6.6.1 Other Safety Analyses

Safety analyses include the following:

- All causality AEs
- All causality AEs (Grades 3–5)
- All causality SAEs
- AEs and SAEs leading to atezolizumab interruption or discontinuation
- AESIs
- irAEs
- Causes of deaths
- Changes from baseline in vital signs during and following atezolizumab administration
- Changes from baseline in clinical laboratory results during and following atezolizumab administration
- Concomitant medications

AEs will be displayed in standard frequency tables according to overall frequency and severity. Time to first incidence of AEs, SAEs, AEs (Grades 3–5) and irAEs will be estimated using the Kaplan-Meier approach. AEs and laboratory parameters will be assessed by the investigator according to the National Cancer Institute Common Terminology Criteria, Version 4.0 (NCI CTC v4.0). AEs and/or SAEs will be coded and analyzed by “preferred terms” according to the Medical Dictionary for Regulatory Activities (MedDRA) and evaluated descriptively

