- r. If available, pre-treatment FFPE tumor tissue (most recent sample) for PD-L1 testing and exploratory biomarkers. Most recent archival sample or a sample obtained during screening should be submitted if available (1 FFPE tissue block or 5–10 slides).
- s. From patients who received anti-PD-1 therapy, sites are highly encouraged to provide archival FFPE tissue (prior anti-PD1 therapy) and an FFPE tissue biopsy obtained during screening (archival and screening tissue sample).
- t. Ten milliliters (10 mL) whole blood for plasma. Not applicable for a site that has not been granted approval for RBR sampling. Performed only for patients at participating sites who have provided written informed consent to participate.
- u. Only to be shipped if the patient is eligible for enrollment.
- v. See [Appendix 4](#).
- w. Concomitant medications include any prescription medications or over-the-counter medications. At screening, any medications the patient has used within the 7 days prior to the screening visit should be documented. At subsequent visits, changes to current medications or medications used since the last documentation of medications will be recorded.
- x. After informed consent has been obtained, but prior to initiation of study drug, only SAEs caused by a protocol-mandated intervention should be reported. After initiation of study drug, all SAEs and AESIs, regardless of relationship to study drug, will be reported until 90 days after the last dose of study drug or initiation of new anti-cancer therapy, whichever occurs first. All other AEs, regardless of relationship to study drug, will be reported until 30 days after the last dose of study drug or initiation of new anti-cancer therapy, whichever occurs first. After this period, the investigator should report any SAEs or AESIs believed to be related to prior study drug treatment. The investigator should follow each AE until the event has resolved to baseline grade or better, the event is assessed as stable by the investigator, the patient is lost to follow-up, or the patient withdraws consent. Every effort should be made to follow all SAEs considered to be related to study drug or study-related procedures until a final outcome can be reported.

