3. STATISTICAL METHODS

The analyses outlined in this SAP supersede those specified in the protocol.

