If no baseline or post-baseline assessment is performed, patients will be censored at the start date of study treatment plus 1 day. Patients without deterioration at the time of clinical cut-off date will be censored at the last time they were known to have not deteriorated.

TTD of the pre-specified symptoms will be summarized using the Kaplan-Meier method. The median time and two-sided 95% CI for the median will also be provided.

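### SAP 3.5.4 names Kaplan-Meier for time to first AESI and irAE but leaves out patients without the event, so it describes onset among affected patients only; the protocol's time to first AE, SAE and Grade 3–5 AE has no SAP analysis

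*SAP*

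**What the plan says.** SAP 3.5.4 measures time to first onset in months from the start of study treatment, names Kaplan-Meier, and covers two categories: AESI and immune-related AE. On patients who never have the event it says only: "Patients without any occurrence of specific AE will not be counted". It gives no censoring date and does not mention death.

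Protocol 6.6.1 lists more: "Time to first incidence of AEs, SAEs, AEs" of Grades 3 to 5, and "irAEs will be estimated using the Kaplan-Meier approach". It leaves nobody out, but it too gives no censoring rule and no handling of death, so the SAP is where both have to be set. SAP 3 states the order of precedence: "The analyses outlined in this SAP supersede those specified in the protocol".

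Elsewhere the SAP says plainly when event-free patients are kept and censored. For symptom deterioration (SAP 3.4.2): "Patients without deterioration at the time of clinical cut-off date will be censored at the last time they were known to have not deteriorated". OS, PFS and duration of response have similar rules.

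Timing is a stated part of the safety objective. Protocol 3.1 says: "Long-term safety will be assessed by monitoring the nature, severity, duration, frequency and timing of atezolizumab-related SAEs and atezolizumab-related irAEs".

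**The concern.** Kaplan-Meier is useful here because patients are at risk for different lengths of time, and those who leave without an event still contribute what was observed. Removing them removes that information. What remains cannot say how likely a treated patient is to have a first AESI or irAE by a given month.

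The other safety outputs do not fill the gap. SAP 3.5.2 and 3.5.3 give crude incidences that do not allow for unequal time at risk, and SAP 3.5.6 deals with time to resolution. For SAEs, whose timing the protocol names in its objective, the SAP has no onset analysis. A reader shown a Kaplan-Meier onset curve would naturally take it as risk in the treated population.

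**Working it through.** The plan gives no figure for this analysis, so there is none to reproduce.

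**Step 1: what the estimator becomes.** Kaplan-Meier is S(t) = Π(1 − d_i/n_i). With N patients who all have the event and none censored, each risk set equals the previous one minus its events. The product telescopes to (number with later onset)/N. With 30 affected patients, S steps through 29/30, 28/30, … to 0. One minus S is the empirical distribution of onset times. It ends at 100% and has a median whether 1% or 30% of patients are affected.

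**Step 2: coverage.**

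| First event | Protocol 6.6.1 | SAP 3.5.4 |
|---|---|---|
| Any AE | yes | absent |
| SAE | yes | absent |
| Grade 3–5 AE | yes | absent |
| irAE | yes | yes, affected patients only |
| AESI | not listed | yes, affected patients only |

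**Step 3: an illustration.** From the documents: accrual over about 18 months (protocol synopsis) and cutoffs about 6 and 30 months after the last enrolment (SAP 2.4). With uniform entry, administrative follow-up A is uniform on 6–24 months at the primary cutoff and on 30–48 months at the final cutoff. Assumed, because the documents give no values:
- Event cumulative hazard H(t) = 0.12(t/12)^k, with k = 1 (constant) or k = 0.5 (front-loaded).
- Exponential end of risk with median 6 months, so μ = ln 2/6 = 0.1155 per month.

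All patients: 1 − exp(−0.12) = 11.3% at 12 months for either k.

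Affected patients only: F(12)/F(∞), where F(t) = ∫₀ᵗ h(u) exp(−H(u)) exp(−μu) P(A>u) du. At the final cutoff:
- k = 1: 0.06200/0.07893 = 78.5%, or 79% (78.55% before rounding); median 5.4 months.
- k = 0.5: 0.07790/0.08512 = 91.5%, or 92%; median 1.8 months.

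Doubling the hazard moves the all-patient figure to 1 − exp(−0.24) = 21.3%. The event-only figure moves only from 78.5% to 80.9% (k = 1) or from 91.5% to 92.3% (k = 0.5). Between the primary and final cutoffs, the event-only median goes from 4.2 to 5.4 months (k = 1) or from 1.5 to 1.8 (k = 0.5).

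**Step 4: a second set of assumptions.** Take crude incidence 5%, exponential onset at rate l, and exponential end of observation at rate c with mean 4 or 8 months, so l = (0.05/0.95)c.
- Mean 4: c = 0.25, l = 0.0132. All patients 1 − exp(−12l) = 14.6%; affected only 1 − exp(−12(l+c)) = 95.7%.
- Mean 8: c = 0.125, l = 0.0066. All patients 7.6%; affected only 79.4%.

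**Step 5: death.** With the step 3 inputs, suppose a share f of ends of risk are deaths and use cumulative incidence. For k = 1 the 12-month value is 0.01/(0.01+fμ) × [1 − exp(−12(0.01+fμ))]: 9.6% at f = 0.25 and 8.2% at f = 0.5, against 11.3% with death censored. For k = 0.5 the values are 10.2% and 9.2%. The handling of death therefore has to be stated.

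**Step 6: the reporting window.** A censoring rule needs an end of observation, and the protocol is not uniform on it. Section 5.1 runs the SAE/AESI window "until 90 days after the last dose of study treatment or until initiation of new anti-cancer therapy, whichever occurs first", and Appendix 1 footnote x agrees: events "will be reported until 90 days after the last dose of study drug or initiation of new anti-cancer therapy, whichever occurs first". Sections 5.3.1, 5.4.2.2 and 5.6 give 90 days without the new-therapy stop. Other AEs are collected for 30 days only. After the window, related SAEs (section 5.6), or related SAEs and AESIs (footnote x), are still to be reported.

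**The case against.** - *The sentence may be loose wording for censoring.* This is possible. But where the SAP keeps event-free patients, it says they are censored and gives the date; here it does neither. The text needs correcting on either reading, for different reasons: exclusion needs no censoring date but yields the wrong quantity, while the benign reading lacks its date. A reader might infer that a date is missing whichever way the sentence is read. That does not follow, because with exclusion there is nobody to censor.
- *Onset among affected patients is a legitimate descriptive summary.* This stands, provided it is labelled as such. Little response to risk is what one expects of a conditional distribution. The shift between cutoffs is also modest if onset is early: 0.3 months in the front-loaded case above.
- *The narrower list may be deliberate, since the SAP supersedes the protocol.* This also stands as a possibility; the complaint is that the SAP neither says so nor gives a reason. A reader might infer that late SAEs are ignored altogether. SAP 3.5.5 does tabulate SAEs and AESIs recorded 30 days after last treatment, although that is not a time-to-onset analysis.
- *The numbers rest on assumed hazards.* They do, and they serve only as illustration.

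**Conclusion.** SAP 3.5.4 is wrong as written. On its likelier reading it does not deliver the Kaplan-Meier time to first incidence in protocol 6.6.1, and three of the protocol's four onset analyses have disappeared without comment. That conclusion rests on the text and on the algebra of step 1, not on any assumed hazard.

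A reader might take 79–92% against 11.3% as the bias of the planned estimate. The documents do not support that: the two figures answer different questions, on assumed inputs, and the gap shows only how far the output could be misread. Nor does the point touch the main safety results. The study is descriptive, and the primary incidences (SAP 3.5.2) and the AE tables (SAP 3.5.3) stand. What is affected is the timing component of the long-term safety objective.

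**What to change.** In SAP 3.5.4:
- Include all safety-population patients and replace the exclusion sentence with a censoring rule.
- Censor event-free patients at the earliest of the end of the reporting window for that event type, last contact, withdrawal or cutoff. The window is 90 days after last dose for SAE, AESI and irAE, and 30 days for any AE and Grade 3–5 AE. Using 90 days for all would credit about 60 days in which non-serious, non-AESI events are not collected.
- Treat death as a competing event with cumulative incidence, or censor at death and say so.
- Reconcile whether new anti-cancer therapy ends the window.
- Say how related SAEs and AESIs reported after the window are handled: outside the curve but listed or tabulated separately so that they are not lost, with a sensitivity analysis that counts them at onset.
- Keep any event-only median as a descriptive, labelled as among affected patients.
- Restore time to first SAE, any AE and Grade 3–5 AE, or state that they are dropped.

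Minor, in SAP 3.5.6: AEs without an end date are censored at the cutoff even if the patient left earlier. Censor them at the earliest of last contact, withdrawal, death or cutoff.

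The cost is a rewording of 3.5.4 and one bullet of 3.5.6, minor programming, one clarification of the reporting window, and a check of which follow-up dates the eCRF holds.
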